## 11. MEDICAL AND PSYCHIATRIC HISTORY

Medical and psychiatric history information will be presented for the SAF set. Medical and psychiatric history conditions are defined as those conditions which stop prior to or at Screening. Conditions will be coded using MedDRA version 20.0 and presented by treatment group, SOC and PT.

Data collected from the Structured Clinical Interview for DSM Disorders-Clinical Trials (SCID-CT) including personal history of traumatic events and Lifetime Illness Characteristics Questionnaire (LICQ) at screening will be presented in listings.

## 12. CONCOMITANT ILLNESSES

Concomitant medical and psychiatric information will be presented for the SAF set. Concomitant illnesses are defined as those conditions which start prior to or at Screening and are ongoing at the date of screening. Concomitant illnesses will be coded using MedDRA version 20.0 and presented by treatment group, SOC and PT.

Information regarding all concomitant illnesses will be listed alongside information for historical medical and psychiatric conditions

## 13. MEDICATIONS

Prior and concomitant medications will be presented using the SAF set and coded using WHO Drug Dictionary (WHODD) 05 June 2017. Summaries will be presented by treatment group, Anatomical, Therapeutic, or Chemical (ATC) level 5 and preferred drug name for prior and concomitant medications separately.

See [APPENDIX 2](#) for handling of partial dates for medications, in the case where it is not possible to define a medication as prior or concomitant, the medication will be classified by the worst case; i.e. concomitant.

- ‘Prior’ medications are medications which started and stopped prior to the first dose of study drug.
- ‘Concomitant’ medications are medications which:
  - started prior to, on or after the first dose of study drug
  - AND ended on or after the date of first dose of study drug or were ongoing at the end of the study.

All information recorded in the eCRF with regards to medications will be listed.

### 13.1. NON-PHARMACOLOGICAL THERAPIES

Use of Cognitive Behavioral Therapy (CBT) will be summarized by treatment group, including a summary of the number of patients who started or stopped CBT whilst receiving study medication.

All Non-pharmacological therapies will be listed.

---

Document:	C:\Users\q718413\Documents\NEP-MDD-201_SAP_v1.0_Final_06Dec2018.docx	Version Number:	1.0
Author:	[name]	Version Date:	06Dec2018

Template No:	CS_TP_BS016 Revision 4	Reference:	CS_WI_BS005
Effective Date:	01Apr2016		

Copyright © 2009, 2010, 2012, 2016 Quintiles Transnational Corp. All rights reserved.  
The contents of this document are confidential and proprietary to Quintiles Transnational Corp. Unauthorized use, disclosure or reproduction is strictly prohibited.

## 14. STUDY MEDICATION EXPOSURE AND COMPLIANCE

The proportion of patients compliant to study medication will be presented for the SAF, FAS and MNRAS analysis sets. A patient will be considered compliant if they received  $\geq 80\%$  and  $< 120\%$  of the expected number of doses during the study. In addition, the proportion of patients who have a dose reduction during week 2 from 80mg to 40mg as permitted in the protocol will be displayed. Compliance and exposure to study drug will also be summarized through descriptive statistics.

### 14.1. DERIVATIONS

Compliance will be calculated according to the following formula:

$$\text{Compliance (\%)} = \left( \frac{\sum \text{Doses received (mg)}}{\sum \text{Expected doses (mg)}} \right) \times 100$$

The expected dosage is 7 daily doses at 40mg followed by 49 daily doses at 80mg. Therefore, the sum of all expected doses for a patient who completes the trial is  $7 \times 40\text{mg} + 49 \times 80\text{mg} = 4200\text{mg}$ .

If a patient discontinues the study early, the sum of all planned doses will be adjusted accordingly so the compliance calculation is not influenced by the time on treatment. The calculation will use the last dose date recorded on the patient disposition page of the eCRF. E.g. if a patient takes their final dose on day 28 the sum of all expected doses will be calculated as the following:  $7 \times 40\text{mg} + 21 \times 80\text{mg} = 1960\text{mg}$ .

In addition, as the protocol allows for a dose reduction during week 2 this will also be accounted for in the compliance calculation. For example, if a patient decides to reduce the daily dosage to 40mg on day 10 and then went on to complete the treatment period, the sum of all expected doses would be calculated as the following:  $7 \times 40\text{mg} + 2 \times 80\text{mg} + 47 \times 40\text{mg} = 2320\text{mg}$ . Any dose reductions after week 2 would be considered a protocol violation and therefore the compliance calculation would not be adjusted.

The sum of all doses received will be calculated using drug accountability data collected on site. The number of capsules dispensed (calculated as the number of bottles dispensed  $\times$  16), the number of capsules returned will be recorded. Each capsule is 40mg, therefore the sum of all doses received will be calculated as:

$$\sum \text{Doses received (mg)} = (\sum \text{Capsules dispensed} - \sum \text{Capsules returned}) \times 40$$

---

Document:	C:\Users\q718413\Documents\NEP-MDD-201_SAP_v1.0_Final_06Dec2018.docx		
Author:	[name]	Version Number:	1.0
		Version Date:	06Dec2018

Template No: CS\_TP\_BS016 Revision 4  
Effective Date: 01Apr2016

Reference: CS\_WI\_BS005

## 15. EFFICACY OUTCOMES

### 15.1. PRIMARY EFFICACY

#### 15.1.1. PRIMARY EFFICACY VARIABLE & DERIVATION

The primary efficacy variable is the change from Baseline in investigator-administered Montgomery-Asberg Depression Rating Scale (MADRS) total score at Week 8. The MADRS is a 10-item rating scale for the evaluation of depressive symptoms. Each item is rated on a 0 to 6 scale with higher scores indicating higher levels of depressive symptoms. Thus, the total score can range from 0 to 60. The MADRS total score will be taken as recorded by the Investigator (i.e., not altered or adjusted) from the vendor dataset provided by Data Management. Change from baseline values will be computed as the MADRS total score at Week 8 – the MADRS total score at Baseline.

#### 15.1.2. MISSING DATA METHODS FOR THE PRIMARY EFFICACY VARIABLE

No missing data imputation is required for the primary analysis, LS means estimates will be adjusted for missing data through the mixed model for repeated measures (MMRM) methods used in the analysis. If data is missing at Week 8 for a patient then they will not be included in the analysis. However, a sensitivity analysis will be conducted with imputed data as described in [section 15.1.4](#).

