## 13 SAMPLE SIZE AND STATISTICAL METHODS

### 13.1 DETERMINATION OF SAMPLE SIZE

The sample size determination was based on the primary endpoint, change from baseline in the Investigator-administered MADRS total score, at Visit 7 (week 8). Approximately 100 patients will be randomized to either BTRX-246040 or placebo in a 1:1 allocation ratio. A sample size of 44 patients per treatment group will provide 75% power to detect a relative effect size of 0.5 on the MADRS total score, based on a two-sample t-test and a significance level of 0.10. All tests are two-sided. To account for patients who may discontinue early and be excluded from the analysis population, a sample size of approximately 50 patients per treatment group (total of 100 patients) will be randomized.

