#### 3.3. CHANGES TO ANALYSIS FROM PROTOCOL

There are no planned changes from the protocol.

---

Document: C:\Users\q718413\Documents\NEP-MDD-201\_SAP\_v1.0\_Final\_06Dec2018.docx  
 Author: [name]  
 Version Number: 1.0  
 Version Date: 06Dec2018

Template No: CS\_TP\_BS016 Revision 4  
 Effective Date: 01Apr2016  
 Reference: CS\_WI\_BS005

Copyright © 2009, 2010, 2012, 2016 Quintiles Transnational Corp. All rights reserved.  
 The contents of this document are confidential and proprietary to Quintiles Transnational Corp. Unauthorized use, disclosure or reproduction is strictly prohibited.

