#### 15.1.3. PRIMARY ANALYSIS OF PRIMARY EFFICACY VARIABLE

The primary objective of this study is to evaluate the effects of BTRX-246040 on symptoms of depression in adult patients with Major Depressive Disorder after 8 weeks of double-blind treatment. To meet this objective the hypothesis that BTRX-246040 is superior to placebo will be tested as follows:

$$H_0: \mu_{\text{BTRX-246040}} = \mu_{\text{placebo}} \text{ VS. } H_a: \mu_{\text{BTRX-246040}} \neq \mu_{\text{placebo}}$$

Where  $\mu$  is the change from baseline in investigator-administered MADRS total score at week 8.

The primary efficacy analysis will be performed for the full analysis set (FAS).

The primary analysis will be a MMRM. A repeated measures analysis refers to a restricted-maximum-likelihood- (REML-) based, MMRM analysis using all the longitudinal observations at each post-baseline visit. The model for this analysis will include the fixed class effects of treatment, investigative site, visit, and the treatment-by-visit interaction as well as the continuous covariate of baseline investigator-administered MADRS total score. An unstructured covariance structure will be used to model the within-patient errors. If the unstructured covariance matrix results in a lack of convergence, the heterogeneous autoregressive variance-covariance structure will be used. The difference in least square means (LS Means) between BTRX-246040 and placebo at Week 8, with corresponding 2-sided 95% confidence intervals and estimated P-values will be presented.

---

Document:	C:\Users\q718413\Documents\NEP-MDD-201_SAP_v1.0_Final_06Dec2018.docx		
Author:	[name]	Version Number:	1.0
		Version Date:	06Dec2018

Template No: CS\_TP\_BS016 Revision 4  
Effective Date: 01Apr2016

Reference: CS\_WI\_BS005

Analysis Plan

---

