#### 15.1.4. SENSITIVITY ANALYSIS OF PRIMARY EFFICACY VARIABLE

The following sensitivity analyses will be conducted on the change from baseline in investigator-administered MADRS total score to ensure robustness of the primary efficacy analysis. The FAS will be used for all sensitivity analyses unless otherwise specified.

- The primary efficacy analysis will be repeated on the PPAS, CAS, and MNRAS analysis sets.
- The MMRM model used for the primary efficacy analysis will be used to analyze the change from Baseline in investigator-administered MADRS total score at each post-Baseline visit. For each visit the difference in LS Means between BTRX-246040 and placebo will be presented alongside the 2-sided 95% confidence interval and P-value.
- ANCOVA will be used to analyze the change in investigator-administered MADRS total score from baseline to week 8, with missing data imputed. The ANCOVA model will include treatment group, investigative site as fixed effects and baseline investigator-administered MADRS total score as a covariate. Only the MADRS total score will be imputed where missing, the individual component scores will not be imputed. Imputation will be performed following visit window remapping. The following two methods of data imputation will be used:
  - Multiple imputation using Rubin's rules with SAS Proc MI and MIANALYSIS.
  - Single imputation by last observation carried forward (LOCF).
- Finally, the change from baseline in the computer-administered MADRS total score will be analyzed using the same method as the primary efficacy analysis.

Forest plots of the treatment difference and confidence intervals will be created for the primary analysis and each of the efficacy analyses.

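### SAP 15.1.2 removes patients without a Week 8 MADRS from the primary analysis, contradicting the all-observations MMRM in SAP 15.1.3 and protocol 13.2.8.1

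*SAP*

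**What the plan says.** SAP 15.1.2 deals with missing data for the primary variable. It says no imputation is needed because "LS means estimates will be adjusted for missing data through the mixed model for repeated measures (MMRM) methods used in the analysis". The next sentence reads: "If data is missing at Week 8 for a patient then they will not be included in the analysis". It then points to a sensitivity analysis with imputed data.

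SAP 15.1.3 defines the primary analysis on the Full Analysis Set (FAS) as an "MMRM analysis using all the longitudinal observations at each post-baseline visit". Protocol 13.2.8.1 specifies the same model, population and data. The FAS (protocol 13.2.2, SAP 5.3) requires one dose taken and one efficacy assessment after it; neither definition mentions Week 8. SAP 3.3 adds: "There are no planned changes from the protocol".

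SAP 15.1.4 lists the supporting analyses. Among them: "The primary efficacy analysis will be repeated on the PPAS, CAS, and MNRAS analysis sets".

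**The concern.** The subject of the disputed sentence is the patient, not the missing Week 8 record. A programmer who follows it deletes a patient seen at Weeks 1, 2, 4 and 6 but not at Week 8. A programmer who follows SAP 15.1.3 keeps that patient's four scores. These are two different primary datasets, and each can be defended from the same final SAP.

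The MMRM is valid under missing-at-random dropout because the earlier scores of patients who leave inform the Week 8 estimate. Under the literal rule those scores are discarded, and the contrast is unprotected if leaving depends on earlier scores differently in the two arms. Some score-related loss is built in: protocol 8.3.1 requires discontinuation at a given MADRS item 10 score, and before another treatment for depression is introduced.

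The by-visit MADRS estimates are also exposed, since SAP 15.1.4 says: "The MMRM model used for the primary efficacy analysis will be used to analyze the change from Baseline in investigator-administered MADRS total score". No carry-over to secondary or exploratory endpoints is claimed. Their missing-data sections (SAP 15.2.2 and 15.3.2) contain no Week 8 exclusion.

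**Working it through.** **1. The texts side by side.** For a patient in the FAS with MADRS at Weeks 1 to 6 and none at Week 8:

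| Source | Patient in the primary analysis? |
|---|---|
| SAP 15.1.2, disputed sentence | No |
| SAP 15.1.2, sentence before it | Yes: the model is said to adjust for missing data |
| SAP 15.1.3; protocol 13.2.8.1 | Yes: FAS, all post-baseline observations |
| SAP 5.3; protocol 13.2.2 | In the FAS: no Week 8 condition |
| SAP 3.3 | Same as the protocol, so yes |

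Under SAP 6.4, an early-termination MADRS on day 51 or later counts as Week 8. The sentence therefore affects patients whose last score falls before day 51, or who missed the Week 8 assessment.

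**2. The plan's own figure.** Protocol 13.1 gives 44 per arm, effect size 0.5, two-sided alpha 0.10 and a two-sample t-test. The noncentrality is 0.5 × √(44/2) = 2.345 on 2 × 44 − 2 = 86 degrees of freedom, and the power is 75.2%. The stated 75% reproduces.

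**3. Data discarded.** No dropout rate is stated. The step from 44 to 50 implies 1 − 44/50 = 12%, or 12 of 100 patients. Suppose they leave in equal numbers after Weeks 1, 2, 4 and 6, with 1, 2, 3 or 4 scores each:

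- scores lost: 12 × 2.5 = 30
- scores kept: 88 × 5 = 440
- share lost: 30/470 = 6.4%

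The simulation in step 4 gives 27.8 to 29.8 of 468 to 470.

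**4. Bias.** Let b be, within an arm, the mean Week 8 change of patients observed at Week 8 minus the mean of all patients in that arm. The literal rule shifts the contrast by b(drug) − b(placebo). The shift cancels when selection is the same in both arms.

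The documents give no SD, correlation or dropout mechanism. The simulation assumed:

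- SD 9 at each visit, with a true difference growing linearly to −4.5 at Week 8 (effect size 0.5)
- two-week correlation 0.6, 0.7 or 0.8, decaying with time
- 12% dropout, after Weeks 1, 2, 4 or 6
- where score-related, log-odds of dropout rising by 0.5, 1.0 or 1.5 per SD of the last score
- 200,000 patients per arm per scenario, with no site or baseline terms

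The literal rule was taken as the mean difference among patients observed at Week 8. The all-observations analysis was maximum likelihood for monotone missing data. Bias is in MADRS points against the complete simulated data; positive means toward zero.

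| Dropout mechanism | Literal rule, Week 8 | Literal rule, Weeks 1–6 |
|---|---|---|
| Random | −0.019 to 0.009 | within 0.032 |
| Score-related, centred within arm, same in both | −0.023 to 0.018 | within 0.032 |
| One common score rule | 0.016 to 0.202 | 0.023 to 0.267 |
| Score-related on placebo only | 0.185 to 0.849 | 0.308 to 1.167 |
| Score-related on drug only | −0.203 to −0.876 | −0.308 to −1.190 |

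The all-observations analysis stayed within 0.023 at Week 8 and 0.020 at Weeks 1–6 in every scenario.

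**5. Cross-check at trial size.** A separate simulation used 50 per arm, 4,000 replicates, a true standardized difference of −0.50, correlation 0.7 between adjacent visits and nominal dropout of 12% to 30%. With score-related dropout of the same form in both arms, the Week-8-only estimate was −0.46 to −0.48. It was −0.39 to −0.43 for placebo only and −0.59 for drug only. All-data likelihood gave −0.49 to −0.51 throughout.

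**The case against.** The strongest reply is that the documents already settle the matter. The section that defines the primary analysis names the FAS and all observations, the protocol agrees, and a separate Completers repeat would be almost redundant if the primary analysis were already limited to patients with Week 8. On this view the sentence means only that a missing Week 8 value is not filled in. That is probably the intent. But the sentence says the patient is left out, it stands where a programmer would look for the missing-data rule, and neither document contains a precedence clause. Protocol 13.1 could even be read in its support: "To account for patients who may discontinue early and be excluded from the analysis population". That is a sizing allowance, not an analysis rule.

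Second, the analyses of covariance with multiple imputation and with last observation carried forward keep these patients, and SAP 15.1.4 adds: "Forest plots of the treatment difference and confidence intervals will be created for the primary analysis and each of the efficacy analyses". A discrepancy would be visible. This mitigates the problem, but the primary estimate and p-value would still come from the wrong rule.

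Third, the larger biases need one-arm, score-related dropout. This stands: they illustrate the risk and are not a forecast. Sites are also told to encourage early leavers to complete the Week 8 assessments, so 12% may not be the true missing rate.

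Fourth, SAP 15.1.4 makes the FAS the default for sensitivity analyses, so carry-over to the by-visit estimates is somewhat less certain than for the Week 8 contrast. This also stands.

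**Conclusion.** The contradiction is real and can be seen from the text alone. One sentence in SAP 15.1.2 defines a different primary analysis population from the one in SAP 15.1.3 and the protocol. It must be corrected because it decides which patients enter the primary analysis; that judgement does not rest on the largest simulated shifts.

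Under the assumptions above, the literal rule costs about 12 patients and 6% of post-baseline scores. It does no material harm to the Week 8 contrast when dropout is random or works the same way within each arm. A common score rule shifts the contrast by up to 0.20 points toward zero. One-arm score-related dropout shifts it by 0.19 to 0.88 points on a difference of −4.5, toward zero if on placebo and away from zero if on drug. The sample-size calculation is not in question.

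**What to change.** Delete the sentence in SAP 15.1.2 and state instead that:

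- every FAS patient with a baseline and at least one post-baseline MADRS contributes all observed visits from Week 1 to Week 8, after the windowing in SAP 6.4;
- missing visits, Week 8 included, are not imputed in the primary analysis;
- no patient is excluded because Week 8 is missing.

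The cost is SAP wording only, with no new data and no added analysis. The protocol already says this and needs no amendment. The change should be made before unblinding, so that the choice of dataset cannot depend on the result.

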#### 15.1.3. PRIMARY ANALYSIS OF PRIMARY EFFICACY VARIABLE

The primary objective of this study is to evaluate the effects of BTRX-246040 on symptoms of depression in adult patients with Major Depressive Disorder after 8 weeks of double-blind treatment. To meet this objective the hypothesis that BTRX-246040 is superior to placebo will be tested as follows:

$$H_0: \mu_{\text{BTRX-246040}} = \mu_{\text{placebo}} \text{ VS. } H_a: \mu_{\text{BTRX-246040}} \neq \mu_{\text{placebo}}$$

Where  $\mu$  is the change from baseline in investigator-administered MADRS total score at week 8.

The primary efficacy analysis will be performed for the full analysis set (FAS).

The primary analysis will be a MMRM. A repeated measures analysis refers to a restricted-maximum-likelihood- (REML-) based, MMRM analysis using all the longitudinal observations at each post-baseline visit. The model for this analysis will include the fixed class effects of treatment, investigative site, visit, and the treatment-by-visit interaction as well as the continuous covariate of baseline investigator-administered MADRS total score. An unstructured covariance structure will be used to model the within-patient errors. If the unstructured covariance matrix results in a lack of convergence, the heterogeneous autoregressive variance-covariance structure will be used. The difference in least square means (LS Means) between BTRX-246040 and placebo at Week 8, with corresponding 2-sided 95% confidence intervals and estimated P-values will be presented.

---

Document:	C:\Users\q718413\Documents\NEP-MDD-201_SAP_v1.0_Final_06Dec2018.docx		
Author:	[name]	Version Number:	1.0
		Version Date:	06Dec2018

Template No: CS\_TP\_BS016 Revision 4  
Effective Date: 01Apr2016

Reference: CS\_WI\_BS005

Analysis Plan

---

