### 10.3 METHOD OF ASSIGNMENT TO TREATMENT

Patients who meet all inclusion criteria and are subsequently not excluded by the exclusion criteria will be randomized to double-blind treatment at Visit 2 (baseline) using an interactive web-response system (IWRS). Patients will be randomized in a 1:1 ratio to one of two treatment arms (placebo or BTRX-246040 QD). Randomization will be stratified by anhedonia symptom severity, as indicated by SHAPS total score  $\leq 4$  and total score  $> 4$ . The order in which the PRT and EEfRT administrations are conducted will be assigned via IWRS.

The IWRS will be used to assign bottles containing double-blind investigational product or placebo to each patient. Site personnel may be required to confirm that they have located the correct bottles by entering a confirmation number found on the package label into the IWRS prior to dispensing the bottle(s) to the patient (see [section 10.5](#)).

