##### 13.2.8.1 PRIMARY EFFICACY ANALYSIS

The primary efficacy analysis will be on the change in Investigator-administered MADRS total score from Visit 2 (baseline) to the last visit of the 8-week double-blind treatment period Visit 7 (week 8). The key comparison will be the contrast between BTRX-246040 and placebo at Visit 7 (week 8) from a mixed-model repeated measures (MMRM) analysis. The primary analysis will use the Full Analysis Set.

A repeated measures analysis refers to a restricted-maximum-likelihood- (REML-) based, MMRM analysis using all the longitudinal observations at each post-baseline visit. The model for this analysis will include the fixed class effects of treatment, investigative site, visit, and treatment-by-visit interaction, as well as the continuous, fixed covariates of baseline Investigator-administered MADRS total score. An unstructured covariance structure will be used to model the within-patient errors. If the unstructured covariance matrix results in a lack of convergence, the heterogeneous autoregressive variance-covariance structure will be used. Least-square means (LS Means) for the difference to placebo at Week 8, with corresponding 2-sided 95% confidence intervals will be presented in tabular and graphical displays.

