**Figure 1: Study Design**

Patients will be consented and screened for the study until approximately 100 patients are randomized. Randomization will be performed at Visit 2 (baseline) in a 1:1 ratio to one of two treatment arms (placebo or BTRX-246040 QD) after meeting disease diagnostic criteria for MDD and study inclusion (see section 8). Randomization will be stratified by anhedonia symptom severity, as indicated by a SHAPS total score  $\leq 4$  and  $> 4$ .

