## 7. STATISTICAL CONSIDERATIONS

### 7.1. ADJUSTMENTS FOR COVARIATES AND FACTORS TO BE INCLUDED IN ANALYSES

The following covariates and factors are used in the analyses. For details of their inclusion in the models, see the specific analysis section.

- Baseline score (continuous variable)
- Treatment group (BTRX-246040 or placebo)
- Pooled Investigative Site
- Study visit (Weeks 1 – 8)
- Treatment-by-visit Interaction

If over parameterization means analyses cannot be performed pooling of investigative sites will be considered, if an appropriate pooling is possible, otherwise investigative site will be removed from the analysis.

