15.2.3.7. Response

The difference in the proportion of responders at week 8 between each treatment group will be estimated for each response variable using a logistic regression model with treatment and investigator site as a fixed effect and baseline investigator-administered MADRS total score as a continuous covariate, using Firth's Penalized Likelihood with CI and p-values based on individual Wald tests.

In addition, the number and percentage of patients within each CGI-S and CGI-I result category will be presented by treatment group and visit. Both CGI-S and CGI-I results will be available at the baseline visit, the CGI-I at baseline will refer to the CGI-S assessment at screening. All subsequent CGI-I assessments will refer to the baseline CGI-S assessment.

Results of each response category at week 8 will be listed for all randomized patients. In addition, all CGI-S and CGI-I results will also be listed.

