**15.3.4. SUBGROUP ANALYSIS**

Analysis by the subgroups defined in [section 7.5](#) will be performed on efficacy endpoints according to the following table. The change from baseline to week 8 for each endpoint will be analyzed using the same method as the endpoint in the main analysis. For the anhedonia severity subgroup analysis, that term will be dropped from the model.

---

Document:	C:\Users\q718413\Documents\NEP-MDD-201_SAP_v1.0_Final_06Dec2018.docx		
Author:	[name]	Version Number:	1.0
		Version Date:	06Dec2018
Template No:	CS_TP_BS016 Revision 4	Reference:	CS_WI_BS005
Effective Date:	01Apr2016		

Copyright © 2009, 2010, 2012, 2016 Quintiles Transnational Corp. All rights reserved.  
The contents of this document are confidential and proprietary to Quintiles Transnational Corp. Unauthorized use, disclosure or reproduction is strictly prohibited.

Analysis Plan

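### Randomisation is stratified by SHAPS (≤4, >4), but the primary and main secondary models omit the stratum, and SAP 15.3.4 drops an anhedonia term that most of the models concerned do not contain

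*SAP*

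**What the plan says.** **Design.** Protocol 10.3: "Randomization will be stratified by anhedonia symptom severity, as indicated by SHAPS total score", cut at ≤4 and >4. SAP 3.1 repeats it: "Randomization will be stratified by anhedonia symptom severity, as indicated by a SHAPS total score". No other stratification factor is named, and SAP 7.2 states that centre was not one.

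**Primary model.** Protocol 13.2.8.1: "The model for this analysis will include the fixed class effects of treatment, investigative site, visit, and treatment-by-visit interaction", with baseline MADRS as continuous covariate. SAP 15.1.3 gives the same terms: "The model for this analysis will include the fixed class effects of treatment, investigative site, visit, and the treatment-by-visit interaction".

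**Other models.**
- SAP 15.1.4: "The ANCOVA model will include treatment group, investigative site as fixed effects and baseline investigator-administered MADRS total score as a covariate".
- SAP 15.2.3.7 specifies a "logistic regression model with treatment and investigator site as a fixed effect and baseline investigator-administered MADRS total score as a continuous covariate".
- SAP 7.1 introduces its list with "The following covariates and factors are used in the analyses". The list holds baseline score, treatment, pooled site, visit and treatment-by-visit, with no SHAPS stratum.

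**Subgroups.** SAP 15.3.4 carries each endpoint's main-analysis method into the subgroups and adds: "For the anhedonia severity subgroup analysis, that term will be dropped from the model". Its table applies SHAPS ≤4/>4 to MADRS total score, and SHAPS ≤7/>7 to MADRS total score, PRT and EEfRT.

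**The concern.** Stratified allocation makes the arms alike on SHAPS stratum. If the stratum is prognostic, the treatment difference varies less from trial to trial than a model without the stratum assumes, because that model leaves the between-stratum variance in its residual. The reported standard error and confidence interval are then wider than they need be. The plan adjusts for site, which was not stratified, and leaves out the one factor that was, without giving a reason.

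A prognostic effect is plausible. The protocol introduction links anhedonic symptoms to poorer treatment response, and baseline MADRS captures anhedonia mainly through one item of ten (inability to feel, protocol 11.1.1).

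The 15.3.4 sentence raises a different problem. It presupposes an anhedonia term in the main model, so a programmer could reasonably ask whether the primary MMRM was meant to have one.

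**Working it through.** **Inputs.** Protocol 13.1 gives 44 per arm, effect size 0.5, two-sided alpha 0.10, a two-sample t-test and 75% power. SAP 6.5 labels the 5% level a strong trend. The documents give no association between stratum and outcome. R², the share of Week 8 residual variance that the stratum explains beyond baseline MADRS and site, is therefore an assumption, taken from 0 to 0.10.

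**Plan's own figure.** Non-centrality = 0.5 × √(44/2) = 2.345. The critical t on 86 df is 1.663. Power is 75.2%, which reproduces the stated 75%.

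**Effect of omitting the stratum** (single time point, arms balanced within stratum):
- Overstatement of the standard error = 1/√(1−R²) − 1. At R² = 0.10: 1/√0.90 = 1.054.
- True size = 2Φ(−z/√(1−R²)). At R² = 0.10 and nominal 10%: 2Φ(−1.645/0.949) = 8.3%.
- Power without the term: non-centrality 2.345/√(1−R²) against critical value t/√(1−R²).
- Power with the term: non-centrality 2.345/√(1−R²) against the ordinary critical t on 85 df.

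| R² | SE overstated | Size of 10% test | Size of 5% test | Power at 10%, without / with | Power at 5%, without / with |
|---|---|---|---|---|---|
| 0 | 0% | 10.0% | 5.0% | 75.2 / 75.2% | 64.0 / 64.0% |
| 0.02 | 1.0% | 9.7% | 4.8% | 75.5 / 76.0% | 64.2 / 64.9% |
| 0.05 | 2.6% | 9.1% | 4.4% | 75.8 / 77.1% | 64.4 / 66.2% |
| 0.10 | 5.4% | 8.3% | 3.9% | 76.4 / 79.0% | 64.7 / 68.6% |

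The largest differences are 79.0 − 76.4 = 2.6 points at the 10% level and 68.6 − 64.7 = 3.9 points at the 5% level.

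**Simulation check** (40,000 trials per setting, stratum share 35 to 65%). At R² = 0.10 the size of the 10% test is 8.1 to 8.3% without the term and 9.8 to 10.0% with it. The true sampling SD of the estimate is 0.201 to 0.203 either way. The mean reported standard error is 0.213 without the term and 0.202 with it. The estimate is equally precise in both models; only its reported error differs.

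**Carrying this to the MMRM.** The key contrast is at Week 8. A stratum term held constant across visits removes all of the stratum's Week 8 variance only if the stratum effect is the same at every visit. Suppose instead that the effect grows in proportion to time, with visit correlations of autoregressive 0.6 or 0.8, or exchangeable 0.5 (all assumed). A constant term then removes about 77 to 80% of that variance if SDs are flat, and about 22 to 49% if they rise from 5 to 10. The gains in the table are therefore upper bounds for a visit-constant term.

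**Responder models** (assumed: placebo response 35%, conditional odds ratio 2.5, stratum odds ratio 0.67 to 0.40, 44 per arm, Firth penalty ignored). The odds ratio without the stratum is 2.48 to 2.39. On the log scale the shift is at most ln 2.5 − ln 2.39 = 0.045, about a tenth of the standard error of 0.44. Power differs by 0.3 to 1.6 points.

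**Where an anhedonia term exists to be dropped:**

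| Endpoint in the 15.3.4 table | Anhedonia term in its main model? |
|---|---|
| MADRS total (SAP 15.1.3) | No |
| PRT, all four measures (SAP 15.2.3.9) | No |
| EEfRT completion rates (SAP 15.2.3.10) | No |
| EEfRT preference GEE (SAP 15.2.3.10) | SHAPS 0–14 score, as one of six variables explored in turn; not the stratum |

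Baseline SHAPS is also the covariate in the SHAPS-endpoint MMRM (SAP 15.2.3.6), but that endpoint is not in the subgroup table.

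**The case against.** The case for leaving the model alone is respectable. Protocol and SAP specify the same primary model, so a reader who infers a protocol–SAP conflict would be wrong. A reader might also infer inflated false positives or an underpowered trial. Neither follows: the error is towards conservatism, and on the planning inputs power without the term is 75.2 to 76.4%. The size rests wholly on an assumed R² whose range includes zero. The stratum is not ignored either, since MADRS results are planned by SHAPS ≤4 and >4. All of this stands, and it keeps the point minor.

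Two further objections shape the remedy. A visit-constant term may recover only part of the gain, so the interaction with visit is needed. And the ≤7 subgroup contains the whole ≤4 stratum plus scores 5 to 7, so dropping the stratum there would repeat the omission.

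On 15.3.4, a reader might conclude that the subgroup analyses cannot be programmed. That goes too far: dropping an absent term leaves the model unchanged, so the MADRS and PRT subgroup models are still determined. Nor does the sentence show that the stratum was intended in the primary MMRM. Every statement of that model omits it, and the EEfRT preference series offers another possible referent. What remains is an ambiguity.

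**Conclusion.** The concern holds as a minor mismatch between design and analysis, together with an unclear sentence in SAP 15.3.4. If the stratum predicts Week 8 outcome beyond baseline MADRS and site, the primary analysis reports too wide an interval and tests slightly below its nominal level. The power figures in the table are for one time point at 44 per arm. They bound what the primary MMRM could gain from a visit-constant term, and they fall to nothing if the stratum is not prognostic. The effect on the responder models is negligible. The 15.3.4 ambiguity depends on no numerical assumption and should be settled whichever primary model is kept.

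**What to change.** 1. Add the randomisation stratum (SHAPS ≤4, >4, as recorded in IWRS) as a fixed effect, with its interaction with visit, to the primary MMRM and the other MMRMs. For the SHAPS endpoint, continuous baseline SHAPS may serve as the adjustment.
2. Add it as a fixed effect to the sensitivity ANCOVA and the responder logistic models. List it in SAP 7.1 and align protocol 13.2.8.
3. Rewrite the SAP 15.3.4 sentence. For MADRS, the stratum is dropped within the ≤4, >4 and >7 subgroups, where it does not vary, and kept within ≤7, which spans both strata. The PRT and EEfRT models contain no stratum term. State whether the SHAPS-score series of the EEfRT preference GEE is run within ≤7 and >7.

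If the sponsor keeps the primary model as written, it should give the reason, delete the 15.3.4 sentence and still settle the EEfRT question.

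The cost is one to a few degrees of freedom and wording changes in both documents, with no new data. Protocol 13.2.1 requires an amendment for a change to a principal feature, so one may be needed. The change must be made before unblinding.
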